10.1.4 Pregnancy reporting

If a female trial participant becomes pregnant, the study treatment should be stopped, and the trial participant must be asked to read and sign pregnancy consent form to allow the Study Doctor ask about her pregnancy. To ensure participant safety, each pregnancy occurring after signing the informed consent must be reported to Novartis within 24 hours of learning of its occurrence. The pregnancy should be followed up to determine outcome, including spontaneous or voluntary termination, details of the birth, and the presence or absence of any birth defects, congenital abnormalities, or maternal and/or newborn complications.

Pregnancy should be recorded and reported by the investigator to the Novartis CMO & PS. Pregnancy follow-up should be recorded on the same form and should include an assessment of the possible relationship to the study treatment and pregnancy outcome. Any SAE experienced during pregnancy must be reported.

Pregnancy outcomes should be collected for the female partners of any males who took study treatment in this study. Consent to report information regarding these pregnancy outcomes should be obtained from the mother.

Pregnancy outcomes will be followed-up at the following times:

- 1 month after the estimated date of delivery
- 3 months after the estimated date of delivery (for a live birth only), and
- 12 months after the estimate date of delivery (for a live birth only).

10.1.5 Reporting of study treatment errors including misuse/abuse

Medication errors are unintentional errors in the prescribing, dispensing, administration or monitoring of a medicine while under the control of a healthcare professional, participant or consumer (European Medical Association definition).

Misuse refers to situations where the medicinal product is intentionally and inappropriately used not in accordance with the protocol.

Abuse corresponds to the persistent or sporadic, intentional excessive use of a medicinal product, which is accompanied by harmful physical or psychological effects.

Study treatment errors and uses outside of what is foreseen in the protocol will be recorded on the appropriate eCRF irrespective of whether or not associated with an AE/SAE and reported to Safety only if associated with an SAE. Misuse or abuse will be collected and reported in the safety database irrespective of it being associated with an AE/SAE within 24 hours of Investigator's awareness.

Table 10-1 Guidance for capturing the study treatment errors including misuse/abuse

Treatment error type	Document in Dosing eCRF (Yes/No)	Document in AE eCRF	Complete SAE form
Unintentional study treatment error	Yes	Only if associated with an AE	Only if associated with an SAE
Misuse/Abuse	Yes	Yes	Yes, even if not associated with a SAE

Please see [Section 10.1.1](#) and [Section 10.1.2](#) for more information on definition and reporting requirements of AE and SAE, respectively.

10.2 Additional Safety Monitoring

10.2.1 Liver safety monitoring

To ensure participant safety and enhance reliability in determining the hepatotoxic potential of an investigational drug, a standardized process for identification, monitoring and evaluation of liver events has to be followed.

Please refer to [Table 16-1](#) in [Section 16.1](#) for complete definitions of liver laboratory triggers.

Once a participant is exposed to study treatment, every liver event defined in [Table 16-1](#) should be followed up by the investigator or designated personnel at the trial site, as summarized below. Additional details on actions required in case of liver events are outlined in [Table 16-2](#) and [Table 16-3](#).

- Repeat liver chemistry tests (i.e. ALT, AST, TBL, PT/INR, ALP and G-GT) to confirm elevation. These liver chemistry repeats should be performed using the local laboratory used by the site. Repeated laboratory test results must be reported as appropriate
- If the initial elevation is confirmed, close observation of the participant will be initiated, including consideration of treatment interruption if deemed appropriate.

- Discontinuation of the investigational drug (refer to the Discontinuation of study treatment section, [Section 9.1.1](#)), if appropriate
- Hospitalization of the participant if appropriate
- Causality assessment of the liver event
- Thorough follow-up of the liver event. These investigations can include based on investigator's discretion: serology tests, imaging, and pathology assessments, hepatologist's consultancy; obtaining more detailed history of symptoms and prior or concurrent diseases, history of concomitant drug use, exclusion of underlying liver disease

All follow-up information and procedures performed must be recorded as appropriate in the eCRF.

10.2.2 Renal safety monitoring

Once a participant is exposed to study treatment, the following two categories of abnormal renal laboratory alert values should be assessed during the study period:

- Serum creatinine increase $\geq 25\%$ compared to baseline during normal hydration status
- Any one of the following:
 - Urine protein-creatinine ratio (PCR) $\geq 1\text{g/g}$ or $\geq 100\text{ mg/mmol}$, OR
 - New onset dipstick proteinuria $\geq 3+$, OR
 - New onset dipstick hematuria $\geq 3+$ (after excluding menstruation, urinary tract infection, extreme exercise, or trauma), OR
 - New evidence of clinically significant crystals on microscopy

Abnormal renal event findings must be confirmed within 24-48 hours after the first assessment.

Once a participant is exposed to study treatment, renal laboratory alerts or renal safety events, as defined in [Table 16-4](#), should be monitored and followed up by the investigator or designated trial staff as summarized in [Table 16-5](#).

11 Data Collection and Database management

11.1 Data collection

Designated investigator staff will enter the data required by the protocol into the eCRF. The eCRFs have been built using fully validated secure web-enabled software that conforms to 21 CFR Part 11 requirements. Investigator site staff will not be given access to the Electronic Data Capture (EDC) system until they have been trained. Automatic validation programs check for data discrepancies in the eCRFs, allow modification and/or verification of the entered data by the investigator staff.

The investigator/designee is responsible for assuring that the data entered into eCRF is complete, accurate, and that entry and updates are performed in a timely manner. The Investigator must certify that the data entered are complete and accurate.

After final database lock, the investigator will receive copies of the participant data for archiving at the investigational site.

All data should be recorded, handled, and stored in a way that allows its accurate reporting, interpretation, and verification.

11.2 Database management and quality control

Novartis personnel (or designated contract research organization (CRO)) will review the data entered by investigational staff for completeness and accuracy. Electronic data queries stating the nature of the problem and requesting clarification will be created for discrepancies and missing values and sent to the investigational site via the EDC system. Designated investigator site staff are required to respond promptly to queries and to make any necessary changes to the data.

Concomitant treatments and prior medications entered into the database will be coded using the World Health Organization (WHO) Drug Reference List, which employs the Anatomical Therapeutic Chemical classification system. Medical history/current medical conditions and AEs will be coded using the Medical Dictionary for Regulatory Activities (MedDRA) terminology.

Once all the necessary actions have been completed and the database has been declared to be complete and accurate, it will be locked and made available for data analysis. Any changes to the database after that time can only be made after written agreement by Novartis development management.

11.3 Site monitoring

Before study initiation, at a site initiation visit or at an investigator's meeting, a Novartis representative will review the protocol and data capture requirements (i.e. eSource Direct Data Entry (DDE) or eCRFs) with the investigators and their staff. During the study, Novartis employs several methods of ensuring protocol and GCP compliance and the quality/integrity of the sites' data. The field monitor will visit the site to check the completeness of participant records, the accuracy of data capture / data entry, the adherence to the protocol and to GCP, the progress of enrollment, and to ensure that study treatment is being stored, dispensed, and accounted for according to specifications. Key study personnel must be available to assist the field monitor during these visits. Continuous remote monitoring of each site's data may be performed by a centralized Novartis Clinical Research Associate organization. Additionally, a central analytics organization may analyze data & identify risks & trends for site operational parameters, and provide reports to Novartis clinical teams to assist with trial oversight.

The investigator must maintain source documents for each participant in the study, consisting of case and visit notes (hospital or clinic medical records) containing demographic and medical information, laboratory data, electrocardiograms, and the results of any other tests or assessments. All information on eCRFs must be traceable to these source documents in the participant's file. The investigator must also keep the original ICF signed by the participant (a signed copy is given to the participant).

The investigator must give the monitor access to all relevant source documents to confirm their consistency with the data capture and/or data entry. Novartis monitoring standards require full verification for the presence of informed consent, adherence to the inclusion/exclusion criteria, documentation of SAEs, and of data that will be used for all primary variables. Additional checks of the consistency of the source data with the eCRFs are performed according

to the study-specific monitoring plan. No information in source documents about the identity of the participants will be disclosed.

12 Data analysis and statistical methods

The analysis will be conducted on all participant data at the time the trial ends. Any data analysis carried out independently by the investigator should be submitted to Novartis before publication or presentation.

12.1 Analysis sets

The safety analysis set will include all participants that received any study drug.

Commercially Confidential Information

The PD analysis set will include all participants with no protocol deviations with relevant impact on PD data.

12.2 Participant demographics and other baseline characteristics

The Safety set will be used for the analyses described in this section. Demographic and other baseline data including disease characteristics and smoking status will be summarized descriptively.

Categorical data will be presented as frequencies and percentages. For continuous data, mean, standard deviation (SD), median, minimum, and maximum will be presented.

Relevant medical histories and current medical conditions at baseline will be listed by system organ class and preferred term.

12.3 Treatments

The Safety set will be used for the analyses described in this section. Categorical data will be summarized as frequencies and percentages. For continuous data, mean, SD, median, 25th and 75th percentiles, minimum, and maximum will be presented.

The frequency of DFV890 doses will be displayed for each participant.

Concomitant medications and significant non-drug therapies prior to and after the start of the study treatment will be listed according to the Anatomical Therapeutic Chemical (ATC) classification system.

12.4 Analysis of the primary endpoint(s)/estimand(s)

The primary aim of the study is to assess the efficacy of DFV890 to reduce cold-induced inflammation in participants with FCAS. The fold change in the highest value of total WCC following exposure to a cold challenge vs. pre-challenge levels will be compared between treatment and screening periods. Lower induction of total WCC is considered a favorable outcome. The PD set will be used for the analyses described in this section.

12.4.1 Definition of primary endpoint(s)/estimand(s)

The primary estimand, including the primary endpoint is defined in [Section 2.1](#) of this protocol and is based on the fold change of WCC.

12.4.2 Statistical model, hypothesis, and method of analysis

Commercially Confidential Information

The primary objective will be achieved and DFV890 will be considered efficacious in treating cold-induced inflammation in participants with FCAS if the estimated ratio of fold changes from pre-challenge to highest post-challenge WCC between treatment and screening period is:

1. statistically significant ($p < 0.10$) and
2. less than 80%.

12.4.3 Handling of remaining intercurrent events of primary estimand

Interruption of study treatment for any reason will be ignored.

12.4.4 Handling of missing values not related to intercurrent event

Due to the limited sample size, all available data will be included in the model. This corresponds to assuming a missing at random strategy.

Commercially Confidential Information

12.5 Analysis of secondary endpoints/estimands

12.5.1 Safety endpoints

For all safety analyses, the safety set will be used. All listings and tables will be presented by period.

Adverse events

All information obtained on adverse events will be displayed by period and participant.

Vital signs

All vital signs data will be listed by period, participant, and time and if ranges are available, abnormalities (and relevant orthostatic changes) will be flagged. Summary statistics will be provided by period and time.

ECG

PR, QRS, QT, QTcF, and RR intervals will be obtained from 12-lead ECGs for each participant during the study. ECG data will be read and interpreted locally. All ECG data will be listed by period, participant and time, abnormalities will be flagged. Summary statistics will be provided by period and time.

Clinical laboratory evaluations

All laboratory data will be listed by period, participant, and time and if normal ranges are available abnormalities will be flagged. Summary statistics will be provided by period and time. Shift tables using the low/normal/high/ (low and high) classification will be used to compare baseline to the worst on-treatment value.

12.5.2 Efficacy and/or Pharmacodynamic endpoint(s)

The secondary efficacy objective is to assess the effect of DFV890 on clinical outcomes in participants with FCAS. For the following analyses, the PD set will be used.

Physician global assessment of autoinflammatory disease activity

Summary statistics will be provided for physician global assessment of autoinflammatory disease activity by period and time.

Physician's severity assessment of autoinflammatory disease signs and symptoms

Summary statistics will be provided for physician's severity assessment of autoinflammatory disease signs and symptoms by period and time.

Patient's global assessment of disease activity

Summary statistics will be provided for patient's global assessment of disease activity by period and time.

12.5.3 Patient reported outcomes

Please refer to [Section 12.5.2](#) for detailed information on the patients global assessment of disease activity.

12.6 Analysis of exploratory endpoints

Commercially Confidential Information

Commercially Confidential Information

12.7 Interim analyses

No interim analysis is planned for this trial.

Interim analyses may be conducted to support decision making concerning the current clinical study, the sponsor's clinical development projects in general or in case of any safety concerns.

[figure not shown]
12.8 Sample size calculation

12.8.1 Primary endpoint(s)

Previous results of a cross-over cold challenge design were reported with a maximum mean treatment effect of approximately $-8 \times 10^9 / L$ in WCC and a standard deviation of the difference of approximately $3 \times 10^9 / L$ (Hoffman et al 2004). In the relative scale, the ratio of fold changes from pre-challenge to highest post challenge WCC between treatment and screening period is found to be a minimum of approximately 25%. Thus, assuming that with a treatment ratio (treatment vs screening period) in the geometric mean of fold changes in WCC of at most 50% and a corresponding standard deviation of the logarithmic fold change to be 0.5, 6 participants provide at least 90% probability to fulfill the combined success criterion described in Section 12.4.2.

Figure 12-1 shows the probability of success for a sample size of 6 participants with varying ratios (from 0.25 to 1) and SD equal to 0.5.

Figure 12-1 Probability of success with 6 participants, varying ratio of fold changes, SD=0.5

13 Ethical considerations and administrative procedures

13.1 Regulatory and ethical compliance

This clinical study was designed and shall be implemented, executed and reported in accordance with the ICH Harmonized Tripartite Guidelines for Good Clinical Practice, with applicable local regulations (including European Directive 2001/20/EC, US CFR 21), and with the ethical principles laid down in the Declaration of Helsinki.

13.2 Responsibilities of the investigator and IRB/IEC

Before initiating a trial, the investigator/institution must obtain approval/favorable opinion from the IRB/IEC for the trial protocol, written ICF, consent form updates, participant recruitment procedures (e.g. advertisements) and any other written information to be provided to participants. Prior to study start, the investigator is required to sign a protocol signature page confirming his/her agreement to conduct the study in accordance with these documents and all of the instructions and procedures found in this protocol and to give access to all relevant data and records to Novartis monitors, auditors, Novartis Quality Assurance representatives, designated agents of Novartis, IRBs/IECs, and regulatory authorities as required. If an inspection of the clinical site is requested by a regulatory authority, the investigator must inform Novartis immediately that this request has been made.

13.3 Publication of study protocol and results

The protocol will be registered in a publicly accessible database such as clinicaltrials.gov and as required in EudraCT. In addition, after study completion (*defined as last patient last visit*) and finalization of the study report the results of this trial will be submitted for publication and posted in a publicly accessible database of clinical trial results, such as the Novartis clinical trial results website and all required Health Authority websites (e.g. Clinicaltrials.gov, EudraCT etc.).

For details on the Novartis publication policy including authorship criteria, please refer to the Novartis publication policy training materials that were provided to you at the trial investigator meetings.

Any data analysis carried out independently by the investigator should be submitted to Novartis before publication or presentation.

Summary results of primary and secondary endpoints will be disclosed based upon the global Last Participant Last Visit (LPLV) date, since multinational studies are locked and reported based upon the global LPLV.

13.4 Quality Control and Quality Assurance

Novartis maintains a robust Quality Management System that includes all activities involved in quality assurance and quality control, to ensure compliance with written SOPs as well as applicable global/local GCP regulations and ICH Guidelines.

Audits of investigator sites, vendors, and Novartis systems are performed by auditors, independent from those involved in conducting, monitoring or performing quality control of the clinical trial. The clinical audit process uses a knowledge/risk based approach.

Audits are conducted to assess GCP compliance with global and local regulatory requirements, protocols and internal SOPs, and are performed according to written Novartis processes.

14 Protocol adherence

This protocol defines the study objectives, the study procedures and the data to be collected on study participants. Additional assessments required to ensure safety of participants should be administered as deemed necessary on a case by case basis. Under no circumstances including incidental collection is an investigator allowed to collect additional data or conduct any additional procedures for any purpose involving any investigational drugs under the protocol, other than the purpose of the study. If despite this interdiction prohibition, data, information, observation would be incidentally collected, the investigator shall immediately disclose it to Novartis and not use it for any purpose other than the study, except for the appropriate monitoring on study participants.

Investigators ascertain they will apply due diligence to avoid protocol deviations. If an investigator feels a protocol deviation would improve the conduct of the study this must be considered a protocol amendment, and unless such an amendment is agreed upon by Novartis and approved by the IRB/IEC and Health Authorities, where required, it cannot be implemented.

16.1 Appendix 1: Liver event and laboratory trigger definitions & follow-up requirements

Table 16-1 Liver event and laboratory trigger definitions

	Definition/ threshold
Liver laboratory triggers If ALT, AST and total bilirubin normal at baseline:	
ALT or AST $>5 \times$ ULNALP $>2 \times$ ULN (in the absence of known bone pathology)Total bilirubin $>3 \times$ ULN (in the absence of known Gilbert syndrome)ALT or AST $>3 \times$ ULN and INR >1.5Potential Hy's Law cases (defined as ALT or AST $>3 \times$ ULN and Total bilirubin $>2 \times$ ULN [mainly conjugated fraction] without notable increase in ALP to $>2 \times$ ULN)Any clinical event of jaundice (or equivalent term)ALT or AST $>3 \times$ ULN accompanied by (general) malaise, fatigue, abdominal pain, nausea, or vomiting, or rash with eosinophiliaAny adverse event potentially indicative of a liver toxicity*
If ALT or AST abnormal at baseline:	
ALT or AST $>2 \times$ baseline or >300 U/L (whichever occurs first)

*These events cover the following: hepatic failure, fibrosis and cirrhosis, and other liver damage-related conditions; non-infectious hepatitis; benign, malignant, and unspecified liver neoplasms
ULN: upper limit of normal

Table 16-2 Follow up requirements for liver laboratory triggers with liver symptoms

ALT	TBL	Liver Symptoms	Action
ALT increase without bilirubin increase:			
If normal at baseline: ALT >3 x ULN	Normal For patients with Gilbert's syndrome: No change in baseline TBL		
 No change to study treatment
If elevated at baseline: ALT >2 x baseline or >300 U/L (whichever occurs first)		None	
 Measure ALT, AST, ALP, GGT, TBIL, INR, albumin, CK, and GLDH in 48-72 hours. Follow-up for symptoms.
ALT increase with bilirubin increase:			
If normal at baseline: ALT >3 x ULN	Normal ALT >8 x ULN	None	
 Interrupt study drug Measure ALT, AST, ALP, GGT, TBIL, INR, albumin, CK, and GLDH in 48-72 hours. Follow-up for symptoms.
If normal at baseline: ALT >3 x ULN	TBL >2 x ULN (or INR >1.5)		
 Initiate close monitoring and workup for competing etiologies.
If elevated at baseline: ALT >2 x baseline or >300 U/L (whichever occurs first)	For patients with Gilbert's syndrome: Doubling of direct bilirubin	None	
 Study drug can be restarted only if another etiology is identified and liver enzymes return to baseline.
If normal at baseline: ALT >3 x ULN		Severe fatigue, nausea, vomiting, right upper quadrant pain	
If elevated at baseline: ALT >2 x baseline or >300 U/L (whichever occurs first)	Normal or elevated		

Table 16-3 Follow up requirements for liver laboratory triggers

Criteria	Actions required	Follow-up monitoring
Total Bilirubin (isolated)		
>1.5 – 3.0 ULN	
 Maintain treatment Repeat liver function tests (LFTs) within 48-72 hours 	Monitor LFTs weekly until resolution ^a to ≤ Grade 1 or to baseline
>3 - 10 × ULN (in the absence of known Gilbert syndrome)	
 Interrupt treatment Repeat LFT within 48-72 hours Hospitalize if clinically appropriate Establish causality Record the AE and contributing factors (e.g. conmeds, med hx, lab) in the appropriate eCRF 	Monitor LFTs weekly until resolution ^a to ≤ Grade 1 or to baseline (ALT, AST, total bilirubin, Alb, PT/INR, ALP and GGT) Test for hemolysis (e.g. reticulocytes, haptoglobin, unconjugated [indirect] bilirubin)
>10 x ULN	
 Discontinue the study treatment immediately Hospitalize the participant Establish causality Record the AE and contributing factors(e.g. conmeds, med hx, lab) in the appropriate eCRF 	ALT, AST, total bilirubin, Alb, PT/INR, ALP and GGT until resolution ^a (frequency at investigator discretion)
Any AE potentially indicative of a liver toxicity*	
 Consider study treatment interruption or discontinuation Hospitalization if clinically appropriate Establish causality Record the AE and contributing factors (e.g. conmeds, med hx, lab) in the appropriate eCRF 	Investigator discretion

^aResolution is defined as an outcome of one of the following: (1) return to baseline values, (2) stable values at three subsequent monitoring visits at least 2 weeks apart, (3) remain at elevated level after a maximum of 6 months, (4) liver transplantation, and (5) death.

*These events cover the following: hepatic failure, fibrosis and cirrhosis, and other liver damage-related conditions; non-infectious hepatitis; benign, malignant and unspecified liver neoplasms ULN: upper limit of normal

Based on investigator's discretion investigation(s) for contributing factors for the liver event can include: serology tests, imaging and pathology assessments, hepatologist's consultancy; obtaining more detailed history of symptoms and prior or concurrent diseases, history of concomitant drug use, exclusion of underlying liver disease.

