9. Clinically significant, suspected active or chronic bacterial (including *Mycobacterium tuberculosis*), viral or fungal infection within 30 days prior to Day 1.

COVID-19 specific: It is highly recommended that testing with polymerase chain reaction or other approved diagnostic methodology for COVID-19 to be completed within 1 week prior to first dosing. If testing is performed, negative test results are required prior to enrolment into the study. Additional testing may occur at the discretion of the investigator. If testing is not performed, the investigator must document their discussion with the participant regarding testing, and the rationale for not testing, in the source documentation. This requirement may be ignored if the pandemic is declared ended by the country where the site is located and resumed if the pandemic recurs.

10. History of malignancy of any organ system (other than localized basal cell carcinoma of the skin or *in situ* cervical cancer), treated or untreated, within the past 5 years prior to Screening, regardless of whether there is evidence of local recurrence or metastases.
11. Absolute peripheral blood neutrophil count of $\leq 1000/\text{mm}^3$ at Screening, Screening Cold Challenge Admission visit and at Day 1 pre-dose.
12. A history of renal disease, including nephrolithiasis, and/or an estimated GFR (eGFR) $\leq 90 \text{ mL/min}/1.73\text{m}^2$ (based on Chronic Kidney Disease Epidemiology Collaboration (CKD-EPI) formula) at Screening, Screening Cold Challenge Admission visit and at Day 1 pre-dose.
13. History of clinically significant liver disease or liver injury as indicated at Screening, Screening Cold Challenge Admission visit and at Day 1 pre-dose by abnormal liver function tests (as defined below) such as aspartate aminotransferase (AST), alanine aminotransferase (ALT), alkaline phosphatase (ALP), or serum bilirubin. The Investigator should be guided by the following criterion:
 - Any single parameter may not exceed 2x upper limit of normal (ULN).
14. History or current diagnosis of ECG abnormalities indicating significant safety risk for participant enrolled in the study such as:

- Concomitant clinically significant cardiac arrhythmias; e.g. sustained ventricular tachycardia, and clinically significant second- or third-degree atrioventricular block without a pacemaker
 - History of familial long QT syndrome or known family history of Torsades de Pointes

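### With baseline ALT or AST above 1.5x and up to 2x ULN, a rise above 3x ULN that stays within 2x baseline meets no numeric trigger in Tables 16-1 and 16-2, even with bilirubin >2x ULN or a measured INR >1.5

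*Protocol*

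**What the plan says.** - **Entry limit (Protocol 5.2, criterion 13).** The guiding rule for liver tests is "Any single parameter may not exceed 2x upper limit of normal (ULN", checked at Screening, at admission for the screening cold challenge and on Day 1 before dosing.
- **Table 16-1.** Under "If ALT, AST and total bilirubin normal at baseline" it lists, among others, ALT or AST >3x ULN with INR >1.5, and potential Hy's Law cases: ALT or AST >3x ULN with bilirubin >2x ULN, mainly conjugated, and without ALP rising above 2x ULN. Under "If ALT or AST abnormal at baseline" it lists only ALT or AST >2x baseline or >300 U/L.
- **Table 16-2.** This table works on ALT alone. The criterion from a normal baseline is >3x ULN; otherwise it is "If elevated at baseline: ALT >2 x baseline or >300 U/L (whichever occurs first". The combined row adds bilirubin >2x ULN or INR >1.5. Its actions are to interrupt the drug, repeat the tests in 48-72 hours and "Initiate close monitoring and workup for competing etiologies". The table is broken in extraction, and I read that action cell as belonging to the combined rows.
- **Table 16-3.** The bilirubin rows are headed "Total Bilirubin (isolated". At >1.5-3.0x ULN the action is "Maintain treatment", with repeat tests and weekly monitoring. Above 3x ULN it is to interrupt, repeat tests and establish causality. A separate row, "Any AE potentially indicative of a liver toxicity", carries no baseline condition.
- **Links.** Section 10.2.1 ties the standard liver follow-up to events defined in Table 16-1. Section 9.1.1 sends liver events to 16.1 for discontinuation. Section 6.5 does not permit dose interruptions.

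**The concern.** The two baseline groups are judged on different scales: multiples of ULN for a normal baseline, multiples of baseline for an abnormal one. Once the baseline is high enough, doubling it requires a higher absolute value than 3x ULN. The abnormal-baseline row has no bilirubin or INR limb to make up the difference.

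The pattern affected is the one the protocol itself labels potential Hy's Law (given the conjugated-fraction and ALP conditions), together with its INR counterpart. From a normal baseline these values start the Section 10.2.1 follow-up and, for ALT, the combined-row actions of Table 16-2. From a baseline near 2x ULN they start neither by rule. At stake is the prescribed response, in particular the competing-cause work-up, which still matters when the abnormal result comes after the last dose.

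**Working it through.** The plan states no figure here to reproduce. The check is one of threshold logic.

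**Inputs.** Baseline *b*, in multiples of ULN, with 1 < *b* ≤ 2 for an abnormal but eligible baseline (criterion 13). I take baseline as the Day 1 pre-dose value, as the SAP does for laboratory shift tables (SAP 7.2); the liver tables do not define it. Peak *p*, also in multiples of ULN.

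**Rules.** The abnormal-baseline rows need *p* > 2*b*, or a value >300 U/L. The normal-baseline combinations need *p* > 3.

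**Uncovered window.** It is (3, 2*b*], with width max(0, 2*b* − 3):

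| Baseline (x ULN) | 2x baseline | Window (x ULN) | Width |
|---|---|---|---|
| 1.5 | 3.0 | none | 0 |
| 1.6 | 3.2 | 3.0-3.2 | 0.2 |
| 1.8 | 3.6 | 3.0-3.6 | 0.6 |
| 2.0 | 4.0 | 3.0-4.0 | 1.0 |

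Up to 1.5x ULN nothing is lost, because any value above 3x ULN already exceeds 2x baseline.

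**The 300 U/L limb.** The documents give no ULN, so it is an assumption. 300 U/L equals 10x ULN at a ULN of 30, 7.5x at 40, 6x at 50, 5x at 60, 4x at 75 and 3x at 100 U/L. The limb therefore enters the window only if ULN exceeds 75 U/L, and closes it completely at 100 U/L.

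**Grid check.** I took baselines 1.51-2.00 and peaks from 3.01 to 2*b*, in steps of 0.01, which gives 2,550 pairs. I crossed these with four bilirubin (x ULN)/INR pairs: 2.5/1.0, 1.0/1.8, 2.5/1.8 and 5/1.8. That makes 10,200 cases. At each ULN tested from 30 to 75 U/L, all 10,200 meet no numeric row of Tables 16-1 or 16-2. At ULN 80 the share is 9,524/10,200 = 93%, at 90 it is 5,576/10,200 = 55%, and at 100 it is 0.

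**Worked cases.** Both enzymes at the same multiple, bilirubin 2.5x ULN, assumed ULN 40 U/L:
- Baseline 0.9, peak 3.9 (156 U/L): meets Table 16-1, if the conjugated-fraction and ALP conditions hold, and the Table 16-2 combined row.
- Baseline 1.5, peak 3.9: meets the >2x baseline rows (3.9 > 3.0).
- Baseline 2.0, peak 3.9: meets none (3.9 < 4.0, and 156 < 300).
- Baseline 2.0, peak 4.1: meets the >2x baseline rows.

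**Time left to act.** The schedule is 2 × 3 + 1 = 7 doses (6.1.3). Table 8-1 is broken in extraction, but the first on-drug chemistry appears to be Day 3 before the morning dose. At most 3 doses then remain: Day 3 morning and evening, and Day 4 morning.

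**The case against.** **Table 16-3 may already cover the bilirubin half.** If ALT within 2x baseline does not count as an ALT trigger, bilirubin is the only trigger-level abnormality, and calling it *isolated* is a fair reading. Bilirubin >3x ULN then already requires interruption, repeat tests and causality assessment. This stands as a reading. It narrows the loss to bilirubin >2x and up to 3x ULN, where treatment continues, and to the INR combination. It does not remove the gap.

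**The lost actions are modest.** What the work-up contains is at the investigator's discretion for any liver event (10.2.1 and 16.1). Interruption conflicts with Section 6.5 and could affect at most 3 doses. Both points stand.

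**The case is rare.** It needs one of about 6 (at most 10) participants to enter above 1.5x ULN, rise less than or exactly 2-fold, and also develop raised bilirubin or INR. INR is measured only where locally routine (Table 8-3). This stands, and it sets the severity.

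**A baseline-relative threshold is a legitimate choice.** That is true of the enzyme criterion on its own. It does not explain why the bilirubin and INR combinations disappear for the same participants.

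**A reader might infer that a Hy's Law case would go undetected.** The documents do not support that. The chemistry panel includes ALT, AST and bilirubin. Clinically significant laboratory values are adverse events (10.1.1), and those must be re-tested (8.4.1). Section 9.1.1 requires discontinuation for a safety risk, or for laboratory abnormalities that the investigator judges to prevent continuing. The liver-AE row of Table 16-3 applies at any baseline. These safeguards rest on judgment, whereas the tables are meant to standardise the response.

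**Conclusion.** The gap is real and narrow, and the point is minor. It exists only for baselines above 1.5x and up to 2x ULN, and spans at most 3.0-4.0x ULN. What is lost is the rule-based response, not detection. For values found on Day 5 or later no dose remains to interrupt, so only the prescribed follow-up and work-up are lost.

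The conclusion rests on four assumptions: the peak is not above 300 U/L (always so if ULN is 75 U/L or less); the other enzyme meets no trigger itself; INR has been measured, for the INR half; and *isolated* in Table 16-3 is taken literally, for the full bilirubin half.

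Two wider conclusions are tempting. One is that every participant with raised baseline enzymes is uncovered; the arithmetic shows no loss on these combinations up to 1.5x ULN. The other is that all normal-baseline triggers should be carried across. Closing this gap does not need that: Table 16-2 already has an elevated-baseline symptom row, and the liver-AE row of Table 16-3 has no baseline condition.

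**What to change.** 1. **Table 16-1:** apply only two triggers whatever the baseline, namely the Hy's Law combination and ALT or AST >3x ULN with INR >1.5. Keep >2x baseline or >300 U/L as an additional trigger for an abnormal baseline.
2. **Table 16-2, elevated-baseline combined row:** replace the ALT criterion with ALT >3x ULN or >2x baseline, whichever is lower (or >300 U/L), together with bilirubin >2x ULN or INR >1.5.
3. **Section 6.5:** reconcile the ban on interruptions with the interrupt action in Table 16-2.

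Do not add AST to Table 16-2, which would change actions at any raised AST baseline. Do not extend the symptom trigger: fatigue/malaise is a scored FCAS symptom (8.3.2), so the trigger could fire on a flare that the cold challenge is meant to provoke.

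**Cost.** Amendment wording and a few more triggers. The rise required becomes 3/*b*: 1.88-fold at baseline 1.6x, 1.67-fold at 1.8x and 1.50-fold at 2.0x ULN, against 2-fold now, and only when bilirubin or INR also qualifies. Raised ALT or AST baselines up to 1.5x ULN are unaffected, since the lower of 3 and 2*b* is then 2*b*. Applied literally, item 1 also reaches participants with normal ALT and AST but raised bilirubin at entry, whom neither Table 16-1 heading names. The bilirubin combination needs no new routine test. The INR combination works only where INR is measured.
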